#### Exclusion Criteria

- The subject has an HS-PGA score of 0 or 1
- The subject has received ILTAC less than 8 days prior to the initial visit.
- The subject does not have capacity to consent to the study.
- The subject has taken systemic steroids at least 4 weeks prior to the time of enrollment.
- The subject has a known allergy or history of adverse reaction to steroids.
- The subject is pregnant.
- Subjects who have received a biologic therapy two weeks before and during the study period.

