##### *Secondary Outcomes*

- Change from baseline in NRS pain scale at days 2, 6, and 14.
- Difference in change from baseline in NRS pain scale at days 2, 6, 14, and 28 between ILTAC-10, ILTAC-20, ILTAC-40.
- Change from baseline in HS-PGA score at week 2 and 4.
- Difference in change from baseline in HS-PGA score at week 2 and 4 between ILTAC-10, ILTAC-20, ILTAC-40.
- Change from baseline in objective markers of inflammation (c-reactive protein [CRP], erythrocyte sedimentation rate [ESR], and interleukin-6 [IL-6]) at week 2 and 4.

- Change from baseline in subjective markers of inflammation (erythema, edema, and suppuration) at week 2 and 4.
- Change from baseline in lesion size at week 2 and 4.
- Difference in change from baseline in lesion size at week 2 and 4 between ILTAC-10, ILTAC-20, ILTAC-40.
- Change from baseline in Patient-Reported Outcomes Measurement Information System (PROMIS) measure of physical functioning at days 2, 6, 14, and 28.
- Difference in change from baseline in PROMIS at days 2, 6, 14, and 28 between ILTAC-10, ILTAC-20, ILTAC-40.
- Proportion of subjects reporting side effects at days 2, 6, 14, and 28.
- Difference in proportion of subjects reporting side effects at days 2, 6, 14, and 28 between ILTAC-10, ILTAC-20, ILTAC-40.
- Baseline patient satisfaction.
- Change from baseline in patient satisfaction at days 2, 6, 14, and 28.
- Serum cortisol and ACTH levels at week 2 and 4.
- Change in serum cortisol and ACTH levels from week 2 to 4.

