Participant eligibility will be assessed according to inclusion and exclusion criteria in 2.0a. A member of the study team will describe the study and answer any of the participant's questions. The participant will then be consented and enrolled. The initial visit and all subsequent visits will include documentation of NRS pain scale (Appendix B), HS-PGA, Hurley Stage (Appendix C), clinical markers of inflammation, and lesion size (as specified in our standard approach to care. Photographs of the lesions will be obtained. The study personnel will administer a patient satisfaction survey and the PROMIS questionnaire, which will take 15 minutes to complete (Appendix D and Appendix F [or Appendix G if pediatric]). Chart review will record demographic information (age, gender, race, ethnicity, smoking status, and BMI) and complete blood count (CBC), basic metabolic profile (BMP), liver function tests (LFT), erythrocyte sedimentation rate (ESR), c-reactive protein (CRP), and interleukin-6 (IL-6). The lab work is a standard of care at the HSC independent of research objectives. The patient will receive an injection, not to exceed 2 mL per anatomic area, in up to 3 anatomic areas (total of 3mL). The patient will be counseled regarding potential side-effects of the treatment (Appendix H) and asked to monitor accordingly. No other changes to the patient's HS medication regimen will be made for the duration of the study.

- Phone Contact 1 (2-day post-treatment)

Since triamcinolone has a half-life of 18 to 36 hours, the initial patient follow-up will be a phone call at 2 days post-injection, lasting 15 minutes. Study personnel will administer a patient satisfaction survey and the PROMIS questionnaire (Appendix D, and Appendix F [or Appendix G if pediatric]). Additionally, patients will be asked if they experienced any side effects, including thinning/atrophy of skin, acneiform lesions, capillary dilation, and/or dyschromia.

- Phone Contact 2 (6 days post-injection)

This 15 minute phone call will be 6 days post-injection and will involve administering the patient satisfaction survey, the PROMIS questionnaire, and questions about side effects.

- Visit 2 (2 weeks post-injection)

- The initial screening visit examination will be repeated at week 2. Additionally, the patient will be asked to identify side effects. A patient

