satisfaction survey as well as the PROMIS questionnaire will also be administered, again lasting 15 minutes. Blood count (CBC), basic metabolic profile (BMP), liver function tests (LFT), erythrocyte sedimentation rate (ESR), c-reactive protein (CRP), and interleukin-6 (IL-6) will be routinely obtained at the two week visit. Serum 8 AM cortisol and ACTH will also be routinely obtained at the two week visit. The two week visit and lab draw are the standard of care for HS patients independent of research objectives.

- Visit 3 (Final visit - 4 weeks post-injection)
  - The initial screening visit examination will be repeated at week 4. Additionally, the patient will be asked to identify side effects. A patient satisfaction survey as well as the PROMIS questionnaire will also be administered, again lasting 15 minutes. Blood count (CBC), basic metabolic profile (BMP), liver function tests (LFT), erythrocyte sedimentation rate (ESR), c-reactive protein (CRP), and interleukin-6 (IL-6) will be routinely obtained at the four week visit. Serum 8 AM cortisol and ACTH will also be routinely obtained at the four week visit. The four week visit and lab draw are the standard of care for HS patients independent of research objectives.

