#### c) Outcome Measures Pertaining to Each Aim

- *Aim 1:* To compare efficacy of ILTAC-10, ILTAC-20, and ILTAC-40 versus placebo, we will measure the change from baseline in pain, objective and subjective markers of inflammation, physical functioning, and lesion size as well as comparing these changes among the different treatment groups. Change from pain baseline will be quantified by comparison of the NRS pain scale across different treatment groups (Appendix B). Objective markers of inflammation include c-reactive protein (CRP), erythrocyte sedimentation rate (ESR), and interleukin-6 (IL-6), which will be obtained from chart review of standard of care initial, 2 week, and 4 week follow-up HS visit. Erythema and edema will be measured clinically based on a 5-point ordinal scale (Appendix E). Suppuration will be measured on a dichotomous scale, by the presence or absence of purulent drainage from the lesion. Physical functioning will be measured by change from baseline in the Patient-Reported Outcomes Measurement Information System (PROMIS) measure of physical functioning. Separate forms will be administered for adult and pediatric participants. A one point change, either positive (improvement) or negative (decline), will be considered clinically meaningful (Appendix F and Appendix G). Lesion size will be measured in centimeters at baseline and during the week 2 and 4 visit.

- *Aim 2:* Side effects of ILTAC-10, ILTAC-20, and ILTAC-40 that will be investigated include thinning/atrophy of the skin, acneiform lesions, capillary dilations, and dyschromia. Hypothalamic-pituitary-adrenal (HPA) axis suppression will be obtained through chart review of standard of care serum 8 AM cortisol and ACTH levels at week 2 and 4 follow-up HS visits. Self-evaluations will be conducted by the patient and documented via telephone interviews. Clinical-evaluations will be conducted at the follow-up visits.
- *Aim 3:* To measure the patient's satisfaction after treatment, we will compare the results from the satisfaction survey between the different treatment groups at baseline, day 2, day 6, week 2, and week 4. The patient satisfaction survey will address disease control, and response to injection (in terms of pain, drainage, and lesion size), and quality of life (Appendix D).

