| HS-PGA   | X          |       |       | X      | X      |
| Treatment: NS,
ILTAC-10,
ILTAC-20 or
ILTAC-40 | X          |       |       |        |        |
| Patient
Satisfaction
Survey                      | X          | X     | X     | X      | X      |
| PROMIS
Survey                                       | X          | X     | X     | X      | X      |
| NRS Pain Scale   | X          | X     | X     | X      | X      |
| Side Effect
Assessment                              |            | X     | X     | X      | X      |

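### Skin side effects are not assessed at enrolment, so older changes can be counted as events and dilute the comparisons between arms

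*Combined protocol and SAP*

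**What the plan says.** - **Outcome (Section 2.0, Secondary Outcomes).** Side effects are summarised as "Proportion of subjects reporting side effects at days 2, 6, 14, and 28", with a further outcome for the difference between the three ILTAC doses. Pain, HS-PGA, lesion size, PROMIS and the inflammation markers in the same list are changes from baseline. Side effects are not.
- **Calendar (Section 5.0 f).** The "Side Effect Assessment" row is empty at enrolment and marked at the four later contacts.
- **Visit 1 (Section 2.0 b).** The initial and later visits "will include documentation of NRS pain scale (Appendix B), HS-PGA, Hurley Stage (Appendix C), clinical markers of inflammation, and lesion size". None of the four named skin changes is on that list. "Photographs of the lesions will be obtained" at this visit, and the calendar repeats the photographs at weeks 2 and 4.
- **Follow-up contacts (Section 2.0 b).** At the first phone call: "Additionally, patients will be asked if they experienced any side effects, including thinning/atrophy of skin, acneiform lesions, capillary dilation, and/or dyschromia". At the week 2 and week 4 visits the screening examination is repeated, and then: "Additionally, the patient will be asked to identify side effects".
- **Aim 2 (Section 2.0 c).** "Clinical-evaluations will be conducted at the follow-up visits".
- **Prior exposure.** The exclusion reads "The subject has received ILTAC less than 8 days prior to the initial visit", so earlier ILTAC is allowed. Section 1.0 says the recruiting centre has used 20-40 mg/mL for hundreds of patients. A separate criterion excludes a known allergy or past adverse reaction to steroids.
- **Analysis (Section 7.0 a).** Presence of side effects is tested by chi-square, with no baseline term.
- **Expectation (Section 2.0, Hypothesis).** The side-effect profile is expected not to differ between ILTAC and saline.

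**The concern.** The four listed effects are skin changes that can outlast the injection that caused them, and the protocol itself attributes them to this drug. The patients come from a centre where the drug is in regular use. HS can also mark the skin: the Hurley stages in Appendix C include scarring. A patient or clinician who notes thin or discoloured skin at week 2 has no enrolment record to show whether it was already there.

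Counting older changes has two effects. It raises the reported rate in every arm. It also makes the arms look more alike, because the same background is added to each. The second effect matters more here, since similarity to saline is what the protocol expects to find. A result of no difference could then reflect the measurement rather than the drug. The between-dose comparison is affected in the same way.

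**Working it through.** **Inputs from the documents.** 30 per arm (Section 3.0 b), two-sided 0.05 and chi-square (Section 7.0 a). The only power calculation is for pain. It reproduces: SD of change = sqrt(1 + 1 - 2 × 0.1) = 1.342; noncentrality = 1 / (1.342 × sqrt(2/30)) = 2.887 on 58 degrees of freedom; power 0.81021, as in the first row of Table 1. It supplies the sample size and says nothing about side effects.

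**Assumptions, because the documents give no rates.** New-event rates of 0% or 5% on saline and 20% on one ILTAC arm. Background share b of 0, 10% or 20%, equal in all arms.

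**Effect on the contrast.** With true new-event rate p, counting any change gives an observed rate of b + (1-b)p. The observed risk difference is (1-b)(p_ILTAC - p_saline). For 5% vs 20% and b = 20%:
- saline: 0.20 + 0.80 × 0.05 = 24%
- ILTAC: 0.20 + 0.80 × 0.20 = 36%
- the risk difference falls from 15 to 12 points, and the risk ratio from 4.0 to 1.5

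**Counting only new events.** If a patient with background can never have a new event, the rates are (1-b)p: 4% and 16% in the same example. The difference is again 12 points, but the noise is lower. The standard error is sqrt((0.04×0.96 + 0.16×0.84)/30) = 7.6 points, against sqrt((0.24×0.76 + 0.36×0.64)/30) = 11.7 points when any change is counted. The power gain in this model therefore comes from removing background noise. The full 15 points return only if worsening of an existing change is also captured.

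**Power at 30 per arm**, by enumerating all pairs of binomial counts; cells show any change / new events only:

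| New-event rates, test | b = 0 | b = 10% | b = 20% |
|---|---|---|---|
| 0% vs 20%, uncorrected chi-square | 88% | 43% / 81% | 28% / 73% |
| 0% vs 20%, Fisher | 57% | 30% / 46% | 20% / 35% |
| 5% vs 20%, uncorrected chi-square | 45% | 24% / 41% | 17% / 36% |
| 5% vs 20%, Fisher | 24% | 16% / 19% | 11% / 15% |

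With a larger assumed effect of 5% vs 30% (chi-square, b = 20%) the figures are 37% / 67%. The loss is in the same direction in every row, but its size depends heavily on the assumed rates and the test. In the 0% vs 20% case without background, the expected number of events under the null is only 3 per arm, where the uncorrected chi-square is not reliable. The Fisher rows are the safer guide there.

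**The case against.** The strongest reply is that the plan does not tell anyone to count older changes. At Visit 1 patients are counselled about possible side effects and asked to watch for them, and later they are asked what they have experienced. That wording points to the time after injection. This stands in part: older changes can be counted, but not by rule. The phone question sets no start date, however, and the clinical evaluation has no baseline item to compare with.

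Second, lesions are examined and photographed at enrolment and again at weeks 2 and 4, and the assessor is blinded. Visible changes could be compared. But no section uses the photographs to judge side effects, and they cannot correct phone reports of changes that do not show in them.

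Third, a past adverse reaction to steroids excludes a patient. A recorded steroid atrophy or dyschromia might fall under this criterion. Unrecorded or mild local changes might not, and changes from HS itself do not.

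Fourth, the comparison is weak anyway. This is right for most rows of the table: even with no background, three of the four scenarios stay below 80% power. A reader might infer from the first row that one form restores adequate power. The documents give no rates that would support that.

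A reader might also infer that Aim 2 as a whole is biased toward reassurance. That goes too far. The absolute ILTAC rates are inflated and look worse; only the contrasts between arms are pulled toward no difference.

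**Conclusion.** The gap is real and is confirmed by the calendar, the visit descriptions and the outcome definition taken together. Without an enrolment assessment, and with a raw proportion as the outcome, older skin changes can be counted as events. Randomisation keeps the comparison fair on average but leaves the dilution. With a counted background share b, the risk difference is (1-b) of its true size and the absolute rates are too high.

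The size cannot be derived from the documents. Under the assumed rates, at 20% background and 30 per arm, power for any versus only new events runs from 28% vs 73% down to 11% vs 15%. These figures assume equal background in all arms, all of it counted, and no new event possible in a patient with background. If some patients leave out old changes, the loss is smaller. The point rests on the direction of the error and the low cost of removing it, not on any single power figure.

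**What to change.** 1. Add the existing side-effect list (Appendix H: atrophy, acneiform lesions, capillary dilation, dyschromia) to the Visit 1 form and to the enrolment column of the Study Calendar. Complete it before injection for each planned site, using the examination and photographs already scheduled.
2. Define the outcome as a change that is new or worsened since baseline at a treated site, and state that the blinded assessor judges it at weeks 2 and 4 against the enrolment record and photographs. Apply the same definition to the between-dose comparison.
3. Word the day 2 and day 6 phone questions as changes since the study injection.

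The cost is one form and a few minutes at Visit 1, plus the wording changes. It has to be done before injection, because a baseline that was not recorded cannot be fully recovered afterwards. The change will not make the side-effect comparison well powered, so it should still be reported with its uncertainty.

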#### Number of Treatment Groups

This study is a parallel study with 4 treatment groups: normal saline, ILTAC-10, ILTAC-20, or ILTAC-40, receiving 2 mL of assigned treatment in up to 3 anatomic areas (maximum of 3 mL per patient).

#### Randomization and Blinding

The groups will be randomized in a 1:1:1:1 ratio and the total volume injected will be recorded at each visit. Randomization and treatment preparation will be performed by the Montefiore Research Pharmacy. Clinical assessments will be conducted by an assessor blind to the treatment allocation. The assessor will undergo training to achieve consistent, unbiased clinical assessments, including HS-PGA, subjective markers of inflammation, and survey administration. The unblinded study team member will maintain confidentiality with respect to participant allocation.

#### Safety Outcomes

Ongoing monitoring for Adverse Events (AEs), as defined by Albert Einstein College of Medicine's "Reportable Events Policy", will occur throughout the study. Adverse events will be reported to the IRB.

#### Data Safety Monitoring Plan

Monitoring will be performed following the "Data and Safety Monitoring Policy" required by the Albert Einstein College of Medicine Institutional Review Board. The Data Safety Monitoring Committee (DSMC) will consist of [name] and [name]. They will have the responsibility for ensuring data and safety monitoring along with the PI who is ultimately responsible for the ongoing monitoring and safety of clinical protocols. The primary functions of the DSMC are as follows:

1. Review/assure protocol compliance.
2. Review all internal and external serious adverse reports, investigator alerts, action letters, and other safety reports.

3. Implement and determine the adequacy of DSM plans of all approved protocols.

The committee will meet quarterly or more frequently as needed. They will review serious (grade 3 or higher) adverse events from the study. In the event that the DSMC decides that a revision is warranted the committee will immediately notify the PI of the study. The DSMC has the authority to close trials to patient accrual should the risk to patients be excessive or outweigh the potential benefits of the study. All study suspensions and closures will be forwarded to the IRB from the DSMC.

b) Schedule of Study Visits

- Visit 1 (Initial visit)

Participant eligibility will be assessed according to inclusion and exclusion criteria in 2.0a. A member of the study team will describe the study and answer any of the participant's questions. The participant will then be consented and enrolled. The initial visit and all subsequent visits will include documentation of NRS pain scale (Appendix B), HS-PGA, Hurley Stage (Appendix C), clinical markers of inflammation, and lesion size (as specified in our standard approach to care. Photographs of the lesions will be obtained. The study personnel will administer a patient satisfaction survey and the PROMIS questionnaire, which will take 15 minutes to complete (Appendix D and Appendix F [or Appendix G if pediatric]). Chart review will record demographic information (age, gender, race, ethnicity, smoking status, and BMI) and complete blood count (CBC), basic metabolic profile (BMP), liver function tests (LFT), erythrocyte sedimentation rate (ESR), c-reactive protein (CRP), and interleukin-6 (IL-6). The lab work is a standard of care at the HSC independent of research objectives. The patient will receive an injection, not to exceed 2 mL per anatomic area, in up to 3 anatomic areas (total of 3mL). The patient will be counseled regarding potential side-effects of the treatment (Appendix H) and asked to monitor accordingly. No other changes to the patient's HS medication regimen will be made for the duration of the study.

- Phone Contact 1 (2-day post-treatment)

Since triamcinolone has a half-life of 18 to 36 hours, the initial patient follow-up will be a phone call at 2 days post-injection, lasting 15 minutes. Study personnel will administer a patient satisfaction survey and the PROMIS questionnaire (Appendix D, and Appendix F [or Appendix G if pediatric]). Additionally, patients will be asked if they experienced any side effects, including thinning/atrophy of skin, acneiform lesions, capillary dilation, and/or dyschromia.

- Phone Contact 2 (6 days post-injection)

This 15 minute phone call will be 6 days post-injection and will involve administering the patient satisfaction survey, the PROMIS questionnaire, and questions about side effects.

- Visit 2 (2 weeks post-injection)

- The initial screening visit examination will be repeated at week 2. Additionally, the patient will be asked to identify side effects. A patient

satisfaction survey as well as the PROMIS questionnaire will also be administered, again lasting 15 minutes. Blood count (CBC), basic metabolic profile (BMP), liver function tests (LFT), erythrocyte sedimentation rate (ESR), c-reactive protein (CRP), and interleukin-6 (IL-6) will be routinely obtained at the two week visit. Serum 8 AM cortisol and ACTH will also be routinely obtained at the two week visit. The two week visit and lab draw are the standard of care for HS patients independent of research objectives.

- Visit 3 (Final visit - 4 weeks post-injection)
  - The initial screening visit examination will be repeated at week 4. Additionally, the patient will be asked to identify side effects. A patient satisfaction survey as well as the PROMIS questionnaire will also be administered, again lasting 15 minutes. Blood count (CBC), basic metabolic profile (BMP), liver function tests (LFT), erythrocyte sedimentation rate (ESR), c-reactive protein (CRP), and interleukin-6 (IL-6) will be routinely obtained at the four week visit. Serum 8 AM cortisol and ACTH will also be routinely obtained at the four week visit. The four week visit and lab draw are the standard of care for HS patients independent of research objectives.

#### Intralesional Triamcinolone Treatment Administration

While HS patients may have multiple sites of symptomatic disease, participants on this protocol will only receive treatment in up to three anatomic regions. These will generally be the most bothersome lesions to the patient. Networks of sinus tracks or the confluence of multiple nodules will be excluded as target treatment sites.

Treatment will only be administered by the blinded clinician on this study. Additionally, the clinical assessor and the patient will be blinded to the treatment group assigned. The patient will either receive normal saline, ILTAC-10, ILTAC-20, or ILTAC-40. Each lesion will be injected with up to 2 mL in up to 3 anatomic areas. The maximum treatment volume is 3 mL.

